### **2.8.1.1 Adverse events of special interest / grouping of AEs**

Selected AEs will be considered under the heading of adverse events of special interest (AESI) and described in the electronic Case Retrieval Sheet (eCRS). The eCRS that is current at the time of the database lock will be used and AESIs will be identified where the flag Core safety topic risk (SP) = 'Y'. The search criteria for the AESI will be included in the TFL shell document.

AESI will be summarized by category and preferred term for the SAF, and will also be listed.

### **2.8.1.2 Other adverse events analyses**

For the legal requirements of ClinicalTrials.gov and EudraCT, two required tables on TEAEs which are not SAEs with an incidence greater than 5% and on treatment emergent SAEs and SAEs suspected to be related to study treatment will be provided by primary SOC and PT.

If for the same participant, several consecutive AEs (irrespective of study treatment causality, seriousness and severity) occurred with the same primary SOC and PT:

- A single occurrence will be counted if there is  $\leq 1$  day gap between the end date of the preceding AE and the start date of the consecutive AE.
- More than one occurrence will be counted if there is  $> 1$  day gap between the end date of the preceding AE and the start date of the consecutive AE.

For occurrence, the presence of at least one SAE/SAE suspected to be related to study treatment/non-SAE has to be checked in a block e.g., among AEs in a  $\leq 1$  day gap block, if at least one SAE is occurring, then one occurrence is calculated for that SAE.

### **2.8.1.3 Deaths**

All deaths including on-treatment and post-treatment deaths will be summarized by MedDRA SOC and PT. All deaths will be listed. Deaths occurring after the on-treatment period will be highlighted in the listing.

## **2.8.2 Laboratory data**

The summary of laboratory evaluations will be presented for three groups of laboratory tests: hematology, chemistry and urinalysis. Each group will be further subdivided into subgroups and presented as per [Table 5-1](#). Summary statistics for the change from baseline to each time point will be tabulated for each laboratory parameter. Data summaries will be provided in SI units.

In addition, shift tables based on normal ranges will be provided for all parameters in [Table 5-1](#) to compare participants' baseline laboratory evaluation relative to the visit's observed value and to the worst post-baseline value.

Number of participants with newly occurring liver enzyme abnormalities at any time post baseline will be summarized. Newly occurring liver enzyme abnormalities are defined in [Section 5.3.2](#).

All laboratory data will be listed by participant and visit/time point and if normal ranges are available, abnormalities will be flagged.

### **2.8.2.1 Other special laboratory results**

Number and percentage of participants meeting the notable low level criteria in IgG or IgM at least once will be provided. A notably low IgG level is defined as a level that is 20% below the lower limit of normal (LLN) and a notably low IgM level is defined as a level 10% below the LLN. A summary of IgG and IgM less than LLN will be provided. Historical change of IgG and IgM will be summarized. Historical IgG and IgM will not be considered for baseline calculations.

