Tele-visit	Procedures or communications conducted using technology such as telephone or video-conference, whereby the participant is not at the investigative site where the investigator will conduct the trial.

Variable	A measured value or assessed response that is determined in specific assessments and used in data analysis to evaluate the drug being tested in the study.
Withdrawal of consent (WoC)/ Opposition to use of data/biological samples	Withdrawal of consent from the study occurs when the participant explicitly requests to stop use of their data and biological samples (opposition to use data and biological samples) AND no longer wishes to receive study treatment, AND does not agree to further protocol required assessments. This request should be in writing (depending on local regulations) and recorded in the source documentation. Opposition to use data/biological samples occurs in the countries where collection and processing of personal data is justified by a different legal reason than consent.

Amendment 02

Rationale for Amendment

Although IgM and IgG are assessed at baseline, this does not indicate if participants' values were declining, were stable or were inclining when entering the trial. Collection of historical values will allow us to observe trends prior to initiating treatment with ofatumumab.

The purpose of the Amendment 2 is to amend the Schedule of Assessments to include:

Table 8-1: Addition of "Historical IgM and IgG" collection to the screening visit

- Footnote #25 added: Historical IgM and IgG results if available from pre-baseline of IV anti-CD20 treatment (one result pre-infusion) and then any testing done following IV anti-CD20 initiation. This should be recorded once for all participants enrolled or completed and may be collected at any visit.
- Footnote #14: Addition of the word "safety" in front of assessments

Section 8.4.5: Added "If available, historical IgM and IgG values that have been collected prior to screening visit, include one pre-anti-CD20 infusion value, should be recorded including the collection date. This should be recorded for all new, existing, and completed participants, and may be entered at any time-point during the study.

Section 12.5.2 under Clinical laboratory evaluations: Added "In addition, historical change of IgM and IgG will be summarized."

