17. Any of the following abnormal laboratory values as confirmed by the central laboratory prior to first study drug administration:
 - Total or conjugated bilirubin (BIL) greater than 3 times upper limit of normal (ULN) range, unless in the context of Gilbert's syndrome
 - Alkaline phosphatase (ALP) greater than 5 times the ULN range
 - ALT between 1.5 and 5 times the ULN range and an active infection with hepatotropic viruses (Herpes simplex virus, Cytomegalovirus and Epstein-Barr Virus)
 - Serum IgG < 300mg/dL (according to central laboratory range)

- Any other clinically significant laboratory assessment as determined by the Investigator (e.g. significant anemia, neutropenia, thrombocytopenia, signs of impaired bone marrow function)
18. Participants with severe hypoproteinaemia e.g. in nephrotic syndrome.
 19. Participants with any of the following neurologic/psychiatric disorders prior to first study drug administration:
 - Score “yes” on item 4 or item 5 of the Suicidal Ideation section of the Columbia-Suicide Severity Rating Scale (C-SSRS), if this ideation occurred in the past 6 months, or “yes” on any item of the Suicidal Behavior section, except for the “Non-Suicidal Self-Injurious Behavior” (item also included in the Suicidal Behavior section), if this behavior occurred in the past 2 years.
 20. Participants unable or unwilling to undergo MRI scans with gadolinium.

6 Treatment

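### The notably low IgG/IgM count in SAP 2.8.2.1 does not separate participants already low at entry from new cases, so it cannot be read as on-study incidence

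*SAP*

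**What the plan says.** SAP 2.8.2.1 sets the rule: "Number and percentage of participants meeting the notable low level criteria in IgG or IgM at least once will be provided". It defines the IgG threshold thus: "A notably low IgG level is defined as a level that is 20% below the lower limit of normal (LLN"). For IgM the margin is 10%. Two companion outputs follow: "A summary of IgG and IgM less than LLN will be provided", and "Historical change of IgG and IgM will be summarized. Historical IgG and IgM will not be considered for baseline calculations".

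SAP 2.8.2 adds change-from-baseline statistics for each laboratory parameter. It also says that "shift tables based on normal ranges will be provided for all parameters in" Table 5-1, setting baseline against each visit and against the worst post-baseline value. Table 5-1 includes total IgG and total IgM. For liver enzymes the same section uses a conditioned count: "Number of participants with newly occurring liver enzyme abnormalities at any time post baseline will be summarized".

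On entry, Protocol 5.1 requires at least two courses of intravenous ocrelizumab or rituximab. Among the laboratory exclusions in Protocol 5.2 (no. 17) the immunoglobulin item is "Serum IgG < 300mg/dL (according to central laboratory range"); no IgM value is listed. Protocol 4.3 confirms that there is no comparator.

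**The concern.** A count of participants with a low value is usually read as the number who became low on treatment. Here the whole population arrives from B-cell-depleting therapy, and no concurrent arm shows what would have happened without the switch. If some participants enter notably low, an unconditioned count adds them to the new cases and the reader cannot tell the two groups apart in that table. Safety and tolerability after the transition is part of the secondary objective, so the difference affects how the percentage can be used. The sponsor was alert to immunoglobulin history: the rationale for Protocol Amendment 02 says "Collection of historical values will allow us to observe trends prior to initiating treatment with ofatumumab". The notable-low table, however, does not use even the baseline value.

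**Working it through.** The plan states no figure for this count, so there is nothing to reproduce. The check has four steps.

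**1. Is the restriction supplied elsewhere?** Not in the text read.
- SAP 2.8 sets only an upper time limit, the safety cut-off.
- The multiple-assessments rule in SAP 2.4.2 uses every assessment within a visit window for tables of notable abnormalities. Table 2-3 includes a baseline window (day -28 to 1).
- Protocol Table 8-1 schedules IgG and IgM at screening, baseline, Month 1, Month 6 and Month 12. Two of the five scheduled values therefore precede the first dose.
- Even if programming used post-baseline values only, a participant who enters notably low and stays there would still be counted.

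**2. Can an eligible participant already be notably low?**
- IgG: the notable threshold is 0.8 × LLN. It equals the entry floor when LLN = 300 / 0.8 = 375 mg/dL. For any higher LLN there is an eligible band that is already notably low. With assumed LLNs of 500, 600 and 700 mg/dL the thresholds are 0.8 × 500 = 400, 0.8 × 600 = 480 and 0.8 × 700 = 560 mg/dL, so the bands run from 300 up to those values.
- IgM: the notable threshold is 0.9 × LLN, and no numeric entry limit applies.

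**3. Do the shift tables recover the new cases?** They cut at the LLN, not at 0.8 or 0.9 × LLN.
- A participant who moves from just under the LLN to notably low falls in the low-to-low cell, with someone who was notably low throughout.
- A participant who moves from normal to notably low falls in the normal-to-low cell, with someone who drops only slightly below the LLN.
- Neither cell isolates new notable cases. For the summary of values below the LLN, by contrast, the normal-to-low cell at worst post-baseline is exactly what is needed.

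**4. How large could the mixing be?** Let b be the share notably low at baseline and i the new incidence among the rest (both assumed). If all baseline-notable participants are counted, the share shown is b + (1 − b) × i, while the newly occurring rate is i.

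| b | i | Share shown | Newly occurring |
|---|---|---|---|
| 0% | 3% | 0 + 1.00 × 3 = 3.0% | 3% |
| 5% | 3% | 5 + 0.95 × 3 = 7.9% | 3% |
| 20% | 3% | 20 + 0.80 × 3 = 22.4% | 3% |
| 30% | 3% | 30 + 0.70 × 3 = 32.1% | 3% |

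The share of counted participants who were already low is b / [b + (1 − b) × i]. Over b = 5% to 30% and i = 2% to 10%, it runs from 5 / (5 + 9.5) = 34% to 30 / (30 + 1.4) = 96%.

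**The case against.** Much of the needed information is already planned. Baseline IgG and IgM are summarized (SAP 2.3.3), as are change from baseline and historical change. The shift tables cover both immunoglobulins, and all laboratory data are listed by participant and visit. This stands, and it limits the point to the notable thresholds. The summary of values below the LLN needs no change, because the normal-range shift tables already cross baseline with the worst post-baseline value. Means do not identify threshold crossings, however, and a recount from listings is not a planned table.

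The liver-enzyme comparison is selective. The notable vital-sign criteria (Table 2-10) and the absolute ECG criteria (Table 2-9) carry no such condition either. An absolute low count also has its own use, since Protocol 16.3.4 refers to the IgG level itself, whatever the baseline. Both remarks are fair. They show that an unconditioned count is not an error as such, and they argue for splitting the table rather than dropping anyone from it. The SAP does condition on baseline where emergence matters: liver enzymes, treatment-emergent adverse events (SAP 2.8.1) and C-SSRS worsening (SAP 2.8.3.1).

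Entry is not limited by the IgG floor alone. Protocol 5.2 also excludes participants stopping anti-CD20 therapy because of decreased IgG that required intravenous immunoglobulin (2c), those with immunodeficiency syndromes (7), and those with other laboratory findings the investigator judges clinically significant (17). These may lower the baseline share, but none sets a numeric IgM limit or uses the notable thresholds.

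The SAP is silent on timing, so counting one low screening value is a possible reading, not an established one. Amendment 02 also mentions a laboratory paragraph in Protocol 12.5.2 that is not in the text read for this review, so a condition stated there cannot be ruled out.

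**Conclusion.** The point holds as a minor one. As written, the notable-low percentage can combine pre-existing and new cases and should not be read as on-study incidence. No planned table shows new crossings of the 20% and 10% thresholds.

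The size cannot be established from the documents. It is zero if nobody enters notably low, and about 8% to 32% shown against a true 3% under the assumptions above. Those figures illustrate the mechanism and do not predict the result.

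A reader might infer that carry-over from earlier therapy is being reported as an effect of ofatumumab. The documents do not support that: the SAP nowhere attributes the count to the drug, and immunoglobulin levels are not among the listed secondary endpoints. A reader might also infer that Amendment 02 was meant to separate pre-study decline from on-study change. Its stated purpose is narrower, namely to see trends before ofatumumab, and the historical summary serves it. Nor does every IgM value at entry count as notably low; only values at least 10% below the LLN do. The primary endpoint and the sample size are unaffected.

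**What to change.** In SAP 2.8.2.1, state that the notable-low count uses post-baseline values up to the safety cut-off, and present the table by baseline status, for IgG and IgM separately:
- newly notable cases, with participants not notably low at baseline as the denominator;
- participants already notably low at baseline, on a separate row, so that further decline in them stays visible.

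The second row matters because simply removing these participants would hide any worsening in them. The cost is a few words and one extra row per table, with a somewhat smaller denominator for the newly notable rate. No new data are needed.

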## **2.8.3 Other safety data**

### **2.8.3.1 Suicidality evaluations**

The Columbia-Suicide Severity Rating Scale (C-SSRS data) will be mapped into 11 levels (see [Section 5.4.1](#) of the Appendix for details) using the Columbia Classification Algorithm for Suicide assessment (C-CASA) as outlined in Food and Drug Administration (FDA) guidance on suicidality ([FDA, 2012](#)).

#### **Definition of 'all prior history' and 'recent history'**

Suicidality evaluations will be collected once pre-treatment, either at screening or at baseline visits. These assessments will be defined by two components: all prior history and recent history.

**All prior history** will be defined as the assessment result obtained from the *lifetime* assessment, and **recent history** will be defined as the assessment result obtained from the *recent past period* assessment.

## **Data summaries**

The number and percentage of participants with suicidal ideation, suicidal behavior and self-injurious behavior without suicidal intent will be presented. The following 14 events will be included in the summary table:

- Each of the 11 categories listed in [Table 5-2](#).
- Any suicidal ideation or behavior (a 'yes' answer to at least one of the 10 suicidal ideation and behavior questions).
- Any suicidal ideation (answered 'yes' to at least one of the 5 suicidal ideation questions).
- Any suicidal behavior (answered 'yes' to at least one of the 5 suicidal behavior questions).

In addition, the number and percentage of participants with the following post-baseline events will be presented ([Nilsson et al. 2013](#)):

- Worsening suicidal ideation compared to recent history: An increase in the maximum suicidal ideation category at any time post-baseline from the maximum suicidal ideation category during pre-treatment recent history.
- Worsening serious suicidal ideation compared to recent history: An increase in the maximum suicidal ideation category to 4 or 5 at any time post-baseline from not having serious suicidal ideation (categories of 0-3) during pre-treatment recent history.
- Emergence of serious suicidal ideation compared to baseline: A maximum suicidal ideation category of 4 or 5 at any time post-baseline from no suicidal ideation (category 0) during pre-treatment recent history.
- Improvement in suicidal ideation at last on-treatment measurement compared to recent history: A decrease in suicidal ideation score at last on-treatment measurement from pre-treatment recent history.
- Emergence of suicidal behavior compared to all prior history: The occurrence of suicidal behavior (Categories 6-10) at any time post-baseline from not having suicidal behavior (Categories 6-10) prior to treatment (includes “lifetime” and any other assessments prior to treatment taken prior to treatment).

Note: in these definitions, a category of 0 is assigned to a subject without suicidal ideation (i.e., a ‘no’ answer to all suicidal ideation categories).

For those analyses, each participant can only be counted once for each event. However, a participant can be counted in several different events.

Suicidal ideation and behavior data will be listed. Detailed answers to C-SSRS items will be listed separately for participants with any suicidal ideation at any time post-baseline (i.e., a ‘yes’ answer to at least one of the five suicidal ideation questions at any time post-baseline) and for a participant with any suicidal behavior at any time post-baseline (i.e., a ‘yes’ answer to at least one of the five suicidal behavior questions at any time post baseline).

### 2.8.3.2 ECG and cardiac imaging data

ECG data will be collected at screening visit, Day 1 and EOS visit. Clinically significant findings from ECG evaluations will be reported as AEs and included in the analysis of AEs. ECG parameters include: mean heart rate, pulse rate (PR) interval aggregate, QRS duration, QT duration and QT corrected using Fridericia’s correction formula (QTcF).

Descriptive statistics including change from baseline of each ECG parameter will be provided by time point. In addition, the number and percentage of participants meeting the criteria defined in [Table 2-9](#) will be summarized by time point.

**Table 2-9 Criteria for relevant ECG absolute or change from baseline values**

Absolute values criteria	Changes from baseline criteria
Heart rate: HR <40 or HR >120 beats/min	NA
Pulse rate: PR <110 or PR >200 msec	NA
QRS duration: <70 msec or >120 msec	QRS duration: increase >25% compared to baseline
QTcF <350 or >450 msec (males) QTcF <360 or >460 msec (females)	QTcF >500 msec and QTcF increase >60 msec

There will be no cardiac imaging data collected for this study.

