## 2 Statistical methods

### 2.1 Data analysis general information

The statistical analysis outlined in this SAP will be performed by Novartis Business Services (NBS) CONEXTS, using SAS® version 9.4 or higher software, and stored in the Novartis Global Programming and Statistical Environment (GPS).

It is planned that the data from all centers that participate in this protocol will be used for analysis.

For continuous variables, summary statistics will include number of participants (n), mean, standard deviation, minimum, 25th percentile, median, 75th percentile, and maximum.

For categorical variables, frequency counts and percentages will be reported.

Unless otherwise specified, summary statistics tables will include change from baseline.

The study will be divided into two phases (the core and post-treatment safety FU phase) for the purpose of preparing the CSR.

- **Core phase:** The core phase will cover the on-treatment period up Month 12 visit date, or EOS date plus the 30 day Safety Telephone FU for participants who discontinue prematurely. The primary objective will be analyzed for the core phase and will be reported in the analysis CSR. All data up to this date will be reported in the analysis CSR.
- **Post-treatment phase:** The post-treatment phase will cover the post-treatment safety follow-up period which extends from the EOS (+ every 3 months) until the date of B cell repletion for study completers until the participant initiates a commercial MS disease modifying therapy or until the end of the safety follow-up for premature withdrawals. This overlaps with the 30 day Safety Telephone FU. All safety data from the EOS to 30 day Safety Telephone FU will be reported as part of the core phase. Post-treatment phase will be reported in the final CSR. Data collected during the post-treatment safety FU will be listed.

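### SAP Table 2-9 ties the 60 msec QTcF rise to a value above 500 msec, so read literally it never counts how many participants had a QTcF rise above 60 msec

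*SAP*

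**What the plan says.** SAP Section 2.8.3.2 plans two outputs for ECG data. The first is continuous: "Descriptive statistics including change from baseline of each ECG parameter will be provided by time point". Under SAP Section 2.1 the standard list of statistics for continuous variables ends with the 75th "percentile, and maximum". The second is categorical: "the number and percentage of participants meeting the criteria defined in" Table 2-9 will be summarized by time point.

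Table 2-9 has a column for absolute values and a column for changes from baseline. The QTcF entries are:

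- Absolute column: "QTcF <350 or >450 msec (males") and "QTcF <360 or >460 msec (females").
- Change column: "QTcF >500 msec and QTcF increase >60 msec". Neither document gives any other threshold for QTcF change.

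The only other entry in the change column is for QRS: "QRS duration: increase >25% compared to baseline". It has no absolute value attached.

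On timing, the same section says "ECG data will be collected at screening visit, Day 1 and EOS visit". Protocol Section 8.4.2 and Table 8-4 agree: single 12-lead tracings, evaluated locally, with the EOS tracing taken pre-dose at Month 12 and unscheduled tracings allowed. There is therefore one scheduled post-baseline ECG. Section 2.8.3.2 also sends clinically significant ECG findings to the adverse event analysis.

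**The concern.** A change-from-baseline criterion is useful when it picks out participants whose value moved a long way, wherever it ended. The QRS entry works like that. The QTcF entry makes the change count depend on an absolute value, and that value lies well beyond the limits in the neighbouring column. A programmer following the cell as written would produce a row containing only people already counted in the absolute row.

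What is lost is one safety count: the number and percentage of participants with a QTcF rise above 60 msec. Some large rises would appear in no categorical row. Others would appear only as high values, and a by-time-point count does not separate them from participants who were already high at baseline.

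The wording also leaves room for two programs with different output. One reading gives a single joint row; the other gives two separate rows.

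**Working it through.** The documents give no figure for these criteria that could be reproduced, so the check is one of logic.

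**Inputs** (all from SAP Table 2-9 unless noted). Let *b* be the baseline QTcF, which SAP Section 2.1.1.5 defines as the last value before first dose, and *p* the post-baseline QTcF, both in whole msec.

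- Absolute criterion, males: *p* < 350 or *p* > 450.
- Absolute criterion, females: *p* < 360 or *p* > 460.
- Change criterion as written: *p* > 500 and *p* − *b* > 60.

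**Step 1: is the change row contained in the absolute row?** If *p* > 500, then *p* > 450 and *p* > 460. Anyone recorded as male or female who meets the change criterion therefore meets the absolute one. Enumerating whole-msec pairs with *b* from 250 to 600 and *p* from 250 to 650 found 0 exceptions for males and 0 for females.

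**Step 2: which rises above 60 msec meet no criterion?** Take a baseline inside the absolute limits. The rise must be at least 61 msec and *p* must not exceed the upper limit.

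- Males: *b* + 61 ≤ 450, so *b* ≤ 450 − 61 = 389. The baseline range is 350-389 msec.
- Females: *b* + 61 ≤ 460, so *b* ≤ 460 − 61 = 399. The baseline range is 360-399 msec.

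**Step 3: which rises above 60 msec are counted only as high absolute values?** Those with *p* at 451-500 msec (males) or 461-500 msec (females). They exceed the absolute limit but do not pass 500.

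**Step 4: examples.**

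| Sex | Baseline | Post-baseline | Rise | Absolute row | Change row as written | Rise > 60 alone |
|---|---|---|---|---|---|---|
| Male | 380 | 448 | 68 | no | no | yes |
| Female | 390 | 458 | 68 | no | no | yes |
| Male | 430 | 495 | 65 | yes | no | yes |
| Female | 435 | 498 | 63 | yes | no | yes |
| Male | 430 | 505 | 75 | yes | yes | yes |

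All five rises exceed 60 msec. The change row as written counts one of them, and the first two meet no criterion in the table.

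**Step 5: where containment fails.** SAP Section 2.3.2 also allows sex to be recorded as unknown or undifferentiated. Table 2-9 gives such a participant no absolute QTcF limit, so the joint row could be the only QTcF row that counts them.

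**The case against.** **The word *and* may be a list.** A value above 500 msec is an absolute criterion placed in the change column, and the adjacent QTcF cell also holds two separate criteria, one for each sex. The author may have meant two events to tabulate. This cannot be ruled out. However, the table writes *or* wherever it offers alternatives (heart rate, PR, QRS and the absolute QTcF limits), so the natural reading of *and* is joint. If a list was meant, the split proposed here is what the sponsor intended, and the cell still needs rewording.

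**A subset is not a fault in itself.** SAP Section 5.3.2 uses nested tiers for liver enzymes (ALT above 3, 5, 10 and 20 times ULN), where a higher tier adds nobody new. The joint QTcF row likewise isolates a more severe group. This stands, and is a reason to allow the row to be kept. The weakness is that it is the only row that uses the change.

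**Other outputs show large rises.** This stands in part. The largest QTcF rise at a time point appears as the maximum in the change-from-baseline summary, and findings judged clinically significant after physician interpretation become adverse events. Neither gives the number of participants above 60 msec.

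**A stronger reading is tempting.** A reader might infer that the table hides large QTcF rises altogether, or that safety reporting fails to detect drug-related prolongation. The documents do not support this. The descriptive and adverse event outputs remain, and rises ending above the absolute limits still appear as high values. Neither document states that the column exists to detect a drug effect. A single-arm trial with one scheduled post-baseline tracing could not attribute a rise to the drug in any case.

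**Conclusion.** The point holds as a minor reporting defect. Taken literally, the QTcF change row is a subset of the absolute row for participants recorded as male or female, so Table 2-9 yields no count of QTcF rises above 60 msec. The rises left with no categorical flag are a limited group: baselines of 350-389 msec in males or 360-399 msec in females, with a final value still inside the limits.

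This rests on three assumptions: *and* is a joint condition, values are in whole milliseconds, and the baseline lies within the absolute limits. How many participants would be affected cannot be estimated, because the documents give no QTcF distribution.

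ECG is a safety assessment here, not a primary or secondary endpoint. The primary endpoint and the sample size are untouched.

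**What to change.** Split the QTcF change cell in Table 2-9 into two separately tabulated criteria, using the SAP's own thresholds:

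- Absolute column: QTcF > 500 msec, in addition to the existing sex-specific limits.
- Change column: QTcF increase from baseline > 60 msec, standing alone as the QRS entry does.

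The joint condition may be kept as a further, explicitly labelled severity tier. State in Section 2.8.3.2 that each criterion is counted separately.

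The cost is one edited cell and one extra row in the ECG output, or two extra rows if the joint tier is kept. No new data are needed, since QTcF and its change from baseline are already derived for the descriptive summary. As the cell gives the 500 msec threshold without regard to sex, its own row would also cover participants recorded as unknown or undifferentiated. The change concerns tabulation only and touches no rule for managing participants.
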